Before the neurocognitive training, all participants will participate in a Motivational Interviewing group session to maximize motivation and adherence to the program. In the session, participants will be guided through open questions and empathic reflections and affirmations to promote change talk. Participants will share their personal aims to reduce weight, improve their diet and increase their level of physical activity. Further, participants will talk about obstacles they have had on previous occasions, their expectations, and their motivations in regards to weight loss. When needed, information about obesity and nutrition will be provided with the elicit-provide-elicit format. Sessions will end with an individual empathic summary for each participant's interventions.

Importantly, all participants will receive an individualized diet (by a Ph.D. nutritionist) and a physical exercise planning (by a Master's degree physical exercise professional) for the following 6 weeks.

Furthermore, with the aim of equating their knowledge before starting the program, all participants will be provided with 20-minute videos on basic ideas and frequent myths about nutrition and physical exercise. Also, brochures made by the research team about basic nutrition and physical exercise will be provided. Further, participants will have the opportunity if they wish so to attend a group session with a nutritionist and another group session with a physical exercise instructor to ask questions about their individualized diet and physical exercise recommendations and solve any doubt they could have about healthy habits, and thus match and complete relevant information on nutrition and excess weight. These two meetings will be recorded and made available for all participants.

A Whatsapp group will be created for each group of participants to promote their social interactions.

Neurocognitive interventions (experimental and active control groups).

Duration: 4 weeks

Note: The order of phases 1 & 2 will be counterbalanced. One task will be trained in each session, and participants will practice the tasks daily at home for one week (until the next session). Daily training will last approximately 5 minutes. Participants will receive daily reminders to practice via instant messaging on their mobile phones. A weekly pre-post assessment will be conducted for each trained task.

Phase 1: Impulsive training will consist of 2 weekly group sessions of about 60-90 minutes.

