Post-treatment interventions (all groups): Participants will have the opportunity to attend a second group meeting with the nutritionist and another with the physical activity professional to receive information and ask questions about how to maintain long-term healthy habits on diet and physical exercise. These meetings will be recorded and made available for all participants. They will also be provided with new videos with guidelines about how to maintain a healthy long-lasting eating and exercise. The aim is that participants be autonomous and can develop their own diet and exercise planning.

Different strategies will be implemented to improve adherence to intervention protocols throughout the program. First, all groups will attend a motivational interview session to promote adherence to the program. All of the intervention sessions will be opened with an explanatory exposition to ensure that participants understand the task perfectly. In addition, the correct execution of each task will be assured in each session: The Tilt Task app has an initial trial with no-food images to test and practice the task before proceeding with the real trial. Furthermore, in both Tilt Task and Food Trainer task sessions, the researcher will ask participants to show their smartphone screen to ensure that movement is detected correctly. As well, if any participant has problems perceiving colors, the Food Trainer app allows to substitute this variable for another one (continuous vs. discontinuous line). Regarding reflexive training sessions, the researcher will ask the participants to send her the worksheets after the group session ends. Thus, she will be able to check the correct execution and suggest improvements to each participant individually. Also, about the homework compliance, the daily reminders will be sent by Whatsapp (thus, the researcher will be able to check that they are received correctly). Daily training at home will be recorded in different ways: Each practice with Tilt Task and Food Trainer apps will be automatically recorded in the online database; referring to implementation of intentions, participants will have to complete a daily self-registration; Lastly, during the EFT training week, they will have to answer some questions on WhatsApp every day. In addition, to monitor the daily task execution, at the beginning of each intervention session participants will answer a short debriefing about their practice over the previous week.

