a. SF-36 Quality of Life Questionnaire: Total score on this questionnaire will be used to estimate the quality of life in terms of utility. The utility will be estimated based on the tariff validated for Spain (Abellán-Perpignan et al., 2012).

b. Years of life adjusted for quality (QALY). The QALY is the most used measure in economic evaluation. It is a measure composed of years of life and profits (collected from the SF-36) that reflect the quality of life of the population under study. This measure will be used in the cost-utility analysis of the intervention.

c. Body Mass Index (kg / m²). This measure will be used to calculate the cost effectiveness of the neurocognitive training intervention.

d. Cost of health resources that the participants spend (visits to primary care, urgencies, hospital admissions, and medicines consumed).

e. Cost of the time spent by the personnel in charge of the neurocognitive training sessions. A professional with the category of Clinical Psychology for each session of cognitive training with 5 participants, with 1 hour 30 minutes per session for 5 weeks. The cost per hour will be collected according to the salary of the personnel of health centers and institutions of the Andalusian Health Service.

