Based on Cohen's (1992) rule of thumb, clinical significance of change will be reflected by medium within-group effect sizes ($d \geq .5$).

Mediation and/or moderation analysis will be carried out to study the role of variables related to cognition, affect, stress and non-homeostatic food intake, motivation and personality on the program outcome measures.

In addition, possible differences in the program outcomes will be assessed based on sex and weight classification (overweight and obesity -type I and type II).

All the analyses described will be carried out following an intention to treat strategy (ITT) and analysis per protocol (PP). Corrections will always be considered to control for multiple comparisons.

- For objective 4, the average cost and effectiveness (BMI and QALY) for the 3 groups (intervention, sham and treatment as usual) will be estimated. The ratios of incremental cost effectiveness and incremental utility cost will be calculated as the cost and effectiveness difference (BMI and QALY) for the 3 groups. All the analyses will be carried out according to the methodological recommendations for Spain (López-Bastida et al., 2010). The perspective of the health system will be used, including only direct costs. The uncertainty of the results will be carried out through various deterministic sensitivity analysis (AS) and a probabilistic one using nonparametric bootstrapping methods of 1000 iterations (Luce et al., 2001) that will allow to represent the cost-effectiveness plane and the Acceptability curve. The AIP will estimate the variation that the introduction of neurocognitive training would imply for the budget of the public health system, based on the estimated costs of the alternatives compared and the estimated number of patients expected to benefit from the program. Likewise, univariate and multivariate AS will be performed to analyze different budgetary scenarios based on a possible variation in the cost variables and number of beneficiary patients.

**Only in experimental and active control groups (what is not in italics is done by all three groups: experimental, active control, and control) //* Assessment task

Figure 1: Procedure of the program.

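### The costed training time (90 minutes per participant) does not match the programme delivered: it omits staff work between sessions and counts 5 weeks for four sessions, so the direction of the net cost error is open

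*Combined protocol and SAP*

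**What the plan says.** Section 2.4, part (5), lists two cost inputs. Item d is participants' use of health care. Item e is the "Cost of the time spent by the personnel in charge of the neurocognitive training sessions", with the quantity set as one clinical psychologist "for each session of cognitive training with 5 participants, with 1 hour 30 minutes per session for 5 weeks". The unit price is an hourly salary: "The cost per hour will be collected according to the salary of the personnel of health centers" and institutions of the regional health service. No other cost line is given.

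Section 2.3 describes staff work outside the sessions as part of the training package of the experimental and sham arms:

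- Reminders: "Participants will receive daily reminders to practice via instant messaging on their mobile phones". They go by WhatsApp, and the researcher can see whether they arrive.
- Worksheets: after the two reflexive sessions participants send these in, so that "she will be able to check the correct execution and suggest improvements to each participant individually".
- Daily messages: "during the EFT training week, they will have to answer some questions on WhatsApp every day".

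Sections 2.3 and 3 give the training as 4 weeks with four sessions (weeks 3, 4, 6 and 7). Section 2.3 puts each session at about 60 to 90 minutes; section 3 says about an hour and a half. Week 5 is the intermediate assessment.

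Section 4, objective 4, takes the health-system perspective with direct costs only. It plans to estimate "the average cost and effectiveness (BMI and QALY) for the 3 groups", incremental ratios across the three groups, and a budget impact defined as the change that introducing the training would bring.

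**The concern.** Under a health-system, direct-cost perspective, staff time needed to deliver the training belongs in its cost. The between-session work is presented as a means of securing adherence, so on its face it is delivery rather than outcome assessment. The usual-treatment arm does not receive it, so it falls inside the increment against usual treatment and inside the budget impact. Worksheet feedback is also explicitly individual, so its cost is not spread over a group of five as session time is.

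The quantity that is costed has its own problem: 5 weeks at 1.5 h is more session time than the schedule contains. Both faults sit in the same line and feed objective 4. If item e is followed as written, the staff input to the cost-effectiveness and cost-utility ratios and to the budget impact is a fixed number that matches neither the sessions held nor the work done.

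**Working it through.** **1. The plan's own quantity (section 2.4, item e).** 5 weeks x 1.5 h = 7.5 h per group; 7.5 h / 5 participants = 1.5 h = 90 min per participant. The plan states no total cost, wage or ratio to reproduce.

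**2. Session time on the schedule (sections 2.3 and 3), groups of 5.**

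- 90-min sessions: 4 x 90 / 5 = 72 min per participant; surplus in the costing 90 - 72 = 18 min.
- 60-min sessions: 4 x 60 / 5 = 48 min per participant; surplus 90 - 48 = 42 min.

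**3. Uncosted support time.** The documents give the tasks but no minutes. Assumed: 2 worksheets at 5, 10 or 15 min, plus 28 days of messaging (reminders and checks together) at 0.25, 1 or 2 min per participant.

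- Low: 2 x 5 + 28 x 0.25 = 17 min
- Middle: 2 x 10 + 28 x 1 = 48 min
- High: 2 x 15 + 28 x 2 = 86 min

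**4. Net error = scheduled session time + support time - 90.** A positive value means that item e understates the training time.

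| Session length | Low | Middle | High |
|---|---|---|---|
| 90 min | 72 + 17 - 90 = -1 | 72 + 48 - 90 = +30 | 72 + 86 - 90 = +68 |
| 60 min | 48 + 17 - 90 = -25 | 48 + 48 - 90 = +6 | 48 + 86 - 90 = +44 |

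Break-even is 18 min of support per participant with 90-min sessions and 42 min with 60-min sessions.

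**5. If messaging is handled once per group.** Section 2.3 sets up a WhatsApp group for each group of participants and does not say whether reminders are individual. If the whole messaging allowance is shared by five, it becomes 7/5 = 1.4, 28/5 = 5.6 or 56/5 = 11.2 min. Support is then 11.4, 25.6 or 41.2 min. The net error is -6.6, +7.6 or +23.2 min (90-min sessions) and -30.6, -16.4 or -0.8 min (60-min sessions).

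**6. What the fifth week might be.** A fifth 90-min contact would reproduce 7.5 h. The candidates are the motivational interview, given to all arms, or the week-5 assessment; the documents do not say. If it is the interview and it is costed in every arm, it cancels against usual treatment. The costed increment is then 4 x 90 / 5 = 72 min, and with 90-min sessions the whole omission is an understatement: 17/72 = 24%, 48/72 = 67% or 86/72 = 119% of the costed increment.

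**7. Care common to all arms (section 3).** Motivational interview 90 min, nutrition 60, exercise 60, and two post-treatment meetings of 60 each: 90 + 60 + 60 + 60 + 60 = 330 min per group. In groups of 5 to 6 that is 330/6 = 55 to 330/5 = 66 min per participant, if every meeting uses that group size and is held. Without the interview it is 240/6 = 40 to 240/5 = 48 min. The individual diet and exercise plans come on top, with no time stated.

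**The case against.** A reader might infer that the incremental cost and the budget impact are understated by a definite amount, for example by 24% to 119% of staff time. The documents do not support that. Those percentages use 72 min as the costed base, while item e costs 90 min, and the surplus works the other way. Against 90 min the same assumed support is 17/90 = 19%, 48/90 = 53% or 86/90 = 96% before the surplus is taken off. Once it is, the sign depends on assumed minutes.

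Other points on that side also stand, at least in part:

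- Individual handling is documented only for worksheet feedback.
- App practice is recorded automatically, and the daily questions apply to one week only, so the upper messaging figures may be generous.
- Some checks are done by the researcher and may be trial monitoring rather than routine delivery. Pricing all of it at a psychologist's rate could overstate cost.
- Sham participants receive the same kind of package, so the omission largely cancels in that comparison if both trained arms are costed alike.

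A reader might also infer that leaving out the common care biases the ratios. It does not: care given equally to all arms cancels there. It also cancels in a budget impact defined as a change, provided patients would receive that care anyway.

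The planned sensitivity analyses could vary the session-time input and so cover part of this uncertainty. They do not name the omitted tasks, and neither they nor the bootstrap can recover staff time that was never recorded.

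**Conclusion.** The point holds as a mismatch between what item e costs and what the programme delivers. Two things rest on the text alone: the between-session tasks have no cost line, and 5 weeks does not agree with four sessions. Taken alone, the first lowers the increment against usual treatment and the budget impact. The second adds 18 to 42 min per participant in the other direction.

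The net error runs from -25 to +68 min per participant under the assumed 17 to 86 min of support. Understatement is plausible, particularly with 90-min sessions, but it is not established. It follows for the comparison with usual treatment if sessions last 90 min and the fifth unit is a motivational interview costed in every arm; the documents do not confirm that reading. With no wage, total cost or ratio stated, the effect on the economic conclusion cannot be sized.

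Separately, the planned average cost per group is incomplete. No line clearly covers the nutritionist and exercise-professional work, nor the motivational interview unless it is the fifth unit. All of this concerns objective 4; the BMI analysis is unaffected. It merits correction because staff time is hard to reconstruct afterwards.

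**What to change.** In section 2.4, part (5), item e:

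1. Replace the fixed quantity with logged staff minutes by task and arm: sessions actually held, worksheet feedback, reminders, message checks. Value each at the tariff of the staff who do the work.
2. Record research-only monitoring separately and exclude it from the base case.
3. Reconcile the 5 weeks with the four training sessions, and say what the fifth unit is and in which arms it is costed.
4. Add a cost line for the care common to all arms (motivational interview, nutritionist, exercise professional), to be used in the average cost per group.

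The cost is a short time log and a few lines of plan text. The ratio against usual treatment may become less favourable.

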3. PROCEDURE

All assessments and intervention sessions will be delivered online. Inclusion and exclusion criteria will be checked through the data collected in a questionnaire of sociodemographic and clinical variables. Further, psychopathology exclusion criteria will be tested with two questionnaires to measure depression, anxiety, and stress symptoms as

well as binge eating and bulimia (DASS-21 and QEWP-5), and a short clinical interview by phone and/or information requested by email in those cases where there are doubts about any of the aspects collected through the online instruments.

All candidates who meet the criteria will attend an information meeting about the project in which they will receive written and oral information, and will be asked for their informed consent. Then, participants will be randomly assigned to groups before the pre-treatment assessment sessions. The three groups of the study (intervention, active control and control) will complete all of the evaluations, as well as the follow-ups (see below and Figure 1). Further, all groups will receive the pre-treatment interventions (Motivational Interviewing, nutrition and physical activity sessions). What will differentiate the groups will be, therefore, the treatment: neurocognitive intervention vs. sham vs. usual treatment. The control groups will be offered the treatment sessions (without the assessment components) after the end of the 6-month follow-up.

Sessions will be developed in groups of 5-6 persons. If a participant misses a session he/she can attend another one within 3-4 days. There will be 10 experimental groups of active training = 50 participants; 10 active control groups of sham training = 50 participants; and 10 control groups = 50 participants. The program will comprise 8 weeks including three assessments (pre, intermediate and post-treatment), four intervention sessions, as well as pre-treatment and post-treatment intervention sessions. Also, two follow-up sessions at 3 and 6 months after treatment (see below). Sessions will last about 1 hour and a half.

Sessions will consist of the following (see Figure 1):

1. Informative session (session 1; week 0): All participants will be informed about the aims and the procedure of the research, and they will provide written informed consent.
2. Pre-treatment assessment (session 2; week 1): All participants will complete the following instruments to assess the main and secondary outcomes, and the potential mediators/moderators, exploratory and economic measures: economic and sociodemographic questionnaire; MEDAS; visual analogue scales to evaluate liking, wanting and hunger; food choice task; food liking task; BRIEF-A; IPAQ; DEBQ; FCQ-Tr; PEMS (Coping subscale); RED; DIS; EIEF; WLSE; SOCRATES-00; PSS; mini IPIP; PANAS; UPPS-P; PSRSQ ; FCCS; SF-36, interview about used health resources. The administration order of the tasks will be counterbalanced.
3. Pre-treatment interventions (sessions 3, 4 and 5, week 2):
 - 3.1. Motivational interviewing session: This 90-minute session will be developed in a group format of 5-6 participants.
 - 3.2. Nutrition session: Participants will receive an individualized diet for the following 6 weeks. Videos and brochures about nutrition will be provided, and participants will assist a 60-minute group session with the nutritionist to match and complete relevant information on nutrition and excess weight.
 - 3.3. Physical activity session: Participants will receive physical activity recommendations for the following 6 weeks. Videos and brochures about physical exercise will be provided, and participants will assist a 60-minute group session with the physical exercise instructor to match and complete relevant information on exercise and excess weight.
4. Intervention sessions (sessions 6, 7, 9 and 10; weeks 3, 4, 6 and 7): All sessions will start with Visual Analogue Scales to evaluate hunger, nutrition and physical activity. Each intervention session will be preceded by its pre-treatment evaluation, and followed by its post-treatment evaluation after a week of daily training. The pre and post-treatment evaluation of the impulsive training will be measured by the approach-avoidance bias (with the Tilt-Task app), food choice, the inhibitory control (with the Food Trainer app) and food liking. The pre and post-treatment evaluation of the reflexive training will be

measured by the Now or Later questionnaire for the episodic future thinking training, and the self-registration of nutrition and physical exercise for the implementation of intentions.

5. Intermediate assessment (session 8; week 5): This assessment will allow the comparison between the interventions for the impulsive and reflexive trainings. It will include: pedometer data; Visual Analogue Scales for liking, wanting and hunger; adherence to diet and physical exercise measured with Visual Analog Scales; Healthy eating with VAS; Exercise habits with VAS; registration of BMI; measure of waist and hip circumference, waist-to-hip ratio and waist-to-height ratio; food choice task; food liking task; PEMS (Coping subscale); DIS; EIEF; WLSE; PANAS; CFCS. The administration order of the tasks will be counterbalanced. After the session, participants will fulfill a self-reported diary with 24-hours food intake.

6. Post-treatment assessment (session 11, week 8): To evaluate the effectiveness of the whole intervention program, the measures of the pre-treatment assessment will be repeated, including: pedometer data; MEDAS, Visual Analogue Scales to evaluate liking, wanting and hunger; adherence to diet and physical exercise measured with Visual Analog Scales; Healthy eating with VAS; Exercise habits with VAS; BMI; measure of waist and hip circumference, waist-to-hip ratio and waist-to-height ratio; food choice task; food liking task; IPAQ; FCQ-Tr; PEMS (Coping subscale); RED; DIS; EIEF; WLSE; PANAS; UPPS-P; CFCS; interview about used health resources. The administration order of the tasks will be counterbalanced. After the session participants will fulfill the self-reported diary with 72-hours food intake.

7. Post-treatment interventions (session 12, week 8): After the post-treatment assessment, participants will have the opportunity to have a second 60-minute group meeting with the nutritionist and another with the physical activity professional, and they will be provided with new 20-minute videos about how to maintain a healthy long-lasting eating and exercise.

After all interventions, participants will be asked to complete a debriefing to register their thoughts and subjective experience about the program.

8. Follow-up (sessions 13 and 14; week 20 and week 32): Follow-ups at 3 and 6 months after the intervention will include the instruments to obtain the main and secondary outcome measures: pedometer data; Visual Analogue Scales to evaluate liking, wanting and hunger; adherence to diet and physical exercise measured with Visual Analog Scales; Healthy eating with VAS; Exercise habits with VAS; BMI; measure of waist and hip circumference, waist-to-hip ratio and waist-to-height ratio; IPAQ; FCQ-Tr; PEMS (Coping subscale); RED; PSS; mini IPIP; SF-36; interview about used health resources; 72 hours food intake. The administration order of the tasks will be counterbalanced.

Besides, every month after the end of the treatment, participants will be contacted by email and mobile message to explore possible difficulties in following healthy nutritional and exercise habits, and to ask them about their physical activity and healthy goals achievement. The purpose of this contact is, fundamentally, therapeutic adherence.

Participants will be instructed to eat two hours before all evaluation (pre, intermediate and post-treatment, and the two follow-ups) and neurocognitive sessions. Pre, intermediate and post-treatment assessments will be carried out at the same hour.

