People between 18 and 55 years old will be candidates to participate in the study, with a good command of the Spanish language, a range of BMI between 25 and 39.9 kg/m², and with at least two electronic devices available (one tablet, computer or smartphone to attend the online meeting and one smartphone with a gyroscope to do the training with the apps). All candidates will be screened for medical and psychological disorders and excluded if they have: (i) traumatic, digestive, metabolic or systemic disorders that affect the central nervous system, autonomic or endocrine, (ii) cardiovascular or any other disorders that prevent physical exercise; (iii) psychopathological disorders or presence of severe symptoms in the Depression Anxiety and Stress Scale-21 (DASS-21); (iv) eating disorders or presence of criteria in the Questionnaire on Eating and Weight Patterns-5 (QEWP-5); (v) pharmacological or any other kind of treatment for losing weight at present; (vi) candidates for bariatric surgery; (vii) food conditions that could interfere with the stimulus of the program (allergies, sprue, vegetarianism, veganism); (viii) current pregnancy or breastfeeding (or expected pregnancy in the following six months); (ix) weight loss $>5\%$ on the 3 months previous to the program; (x) use of medication that affects weight; (xi) frequent use of alcohol or other drugs that affects food intake.

Sampling context:

The recruitment will be carried out through social media and the web of the project.

Randomization and blinding:

A randomization (minimization) through the software Minimizer® will be performed to avoid imbalances between the groups in age, sex, and BMI (Stout et al., 1994). The psychologists that conduct the assessments (screening, evaluation sessions and follow-ups) will be blinded to the group allocation during the whole project. Moreover, since all assessments will be computerized and online, they are not subject to the biases of the evaluator. Further, all participants will be blind to their condition. Also, the people who perform the statistical analyses will be blind to the condition of the groups, through the coding of the interventions. Only the therapist performing the interventions will not be blind to the allocation of the participants.

2.3. Interventions:

Pre-treatment interventions (all groups).

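### Participants are treated in 10 session groups per arm, but the planned ANOVA treats them as independent; if change is correlated within session groups, between-arm tests reject too often

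*Combined protocol and SAP*

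**What the plan says.** Section 2.2 allocates 150 people individually, by minimisation, to three arms of 50. Section 3 then organises delivery in small groups: "Sessions will be developed in groups of 5-6 persons". For the trained arm it states "There will be 10 experimental groups of active training = 50 participants", and it sets the same 10 groups and 50 people for the sham and usual-treatment arms. Each session group therefore lies wholly inside one arm.

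Every arm has group motivational interviewing ("This 90-minute session will be developed in a group format of 5-6 participants") and a messaging group: "A Whatsapp group will be created for each group of participants to promote their social interactions". The experimental and sham arms also have four group training sessions, two per phase (for phase 1, "Impulsive training will consist of 2 weekly group sessions of about 60-90 minutes"). Movement between groups is possible: "If a participant misses a session he/she can attend another one within 3-4 days".

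Section 4 plans a two-way repeated-measures ANOVA, with BMI at four time points for objective 1. Section 2.2 gives 105 participants from G-Power, raises this to 150, and says that power is then assured even after a 30% loss. Neither section mentions session group, an ICC or a design effect. The nearest text is a general statement in section 4 that the methods will suit the characteristics of the data; it does not refer to grouping.

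**The concern.** Individual randomisation makes participants independent at allocation. It does not keep them independent once they share sessions and a chat group designed to make them interact. Because session groups are nested in arms, any shared shift in a group's outcome adds to the variance of the arm mean. An ANOVA with participants as the only unit does not count that variance in full. Its standard errors are then too small and its between-arm tests reject too often, for BMI change and for the secondary outcomes alike. The sample-size statement has the same gap, since its assurance about power after loss assumes no correlation within session groups without saying so.

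**Working it through.** **Inputs from the plan.** 3 arms, 10 session groups per arm, 50/10 = 5 per group on average, alpha 0.05, 105 before loss, 30% loss. **Assumed.** ICC of change 0.02, 0.05 and 0.10; the documents give none.

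**The plan's own figure.** 105/(1 - 0.30) = 150, so the step to 150 reproduces exactly. It is also fully used by the loss: 150 x 0.70 = 105 completers, or 3.5 per session group.

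**Design effect.** DE = 1 + (m - 1) x ICC.
- m = 5: 1.08, 1.20 and 1.40. The true standard error is about the square root of DE times the one reported: 1.04, 1.10 and 1.18.
- m = 3.5: 1.05, 1.125 and 1.25. The 105 completers then carry the information of 105/DE = 100, 93 and 84 independent participants.

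**Exact type I error, three-arm test on change.** Scale the variance of change to 1. The between-arm sum of squares is DE x chi-square(2). The residual sum of squares is DE x chi-square(27) + (1 - ICC) x chi-square(N - 30). Hence

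error = (1 + 2t x DE)^(-27/2) x (1 + 2t x (1 - ICC))^(-(N - 30)/2), with t = Fcrit(2, N - 3)/((N - 3) x DE) and N = 30m.

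For m = 5 and ICC 0.05: Fcrit(2, 147) = 3.058 and t = 3.058/(147 x 1.20) = 0.01733. The factors are 0.577 and 0.143, and their product is 0.0825, or 8.3%. At ICC 0 the formula returns 5.0%, as it should.

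| True error of a nominal 5% test | ICC 0.02 | 0.05 | 0.10 |
|---|---|---|---|
| Three-arm, 5 per group (exact) | 6.2% | 8.3% | 11.8% |
| Three-arm, 3.5 per group (exact) | 5.8% | 7.0% | 9.1% |
| Three-arm, uneven groups after 30% loss (simulated) | 5.9% | 7.3% | 9.6% |
| Three-arm, 5 per group, no clustering in usual treatment (simulated) | 5.8% | 7.1% | 9.4% |
| Three-arm, 30% loss, no clustering in usual treatment (simulated) | 5.6% | 6.5% | 8.0% |
| Arm-by-time ANOVA, four visits, 5 per group (simulated) | 6.0% | 7.9% | 11.4% |
| Arm-by-time ANOVA, four visits, 30% loss (simulated) | 5.6% | 6.9% | 9.2% |
| Pairwise, 5 per group (simulated) | about 6% | about 7% | 9-10% |
| Pairwise, 30% loss (simulated) | about 6% | 6.4% | 8.3% |

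**Remedies (simulated).** Group-mean change by arm kept the error at 4.7-5.1% in all 14 settings tried, and at 4.9-5.1% for pairwise contrasts. A mixed model with one common session-group variance and 27 df gave 3.0-4.6%; it estimated that variance as zero in 10-54% of trials.

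**Price if the ICC is zero.** The ratios of t quantiles are t(27)/t(147) = 1.038 and t(18)/t(98) = 1.059. Simulated mean widths for three-arm intervals rise by about 3% (group means, full groups) to 8% (group means after 30% loss, or the mixed model). Pairwise group-mean intervals are about 5% wider with full groups and about 10% wider after 30% loss.

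**Whole groups lost.** If 15 of 50 are lost at random in an arm, a given group of 5 disappears with probability (15 x 14 x 13 x 12 x 11)/(50 x 49 x 48 x 47 x 46) = 0.00142. Over 30 groups that is about 4% of trials (30 x 0.00142 = 0.043), so 27 and 18 df are not assured.

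**The case against.** The strongest reply is that the ICC may be close to zero. Diets are individual, training is practised daily at home, the apps are used alone, delivery is online, and missed sessions can be made up in another group. The blinding text also refers to one therapist: "Only the therapist performing the interventions will not be blind to the allocation of the participants". All of this stands, and it is why the point is conditional. At ICC 0.02 with full groups the excess is only 1.2 percentage points for the three-arm test and about 1 point pairwise. In the other direction, the messaging group exists to promote interaction, and the motivational session relies on participants sharing aims and obstacles.

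It can also be said that the hypothesis in section 1 is pairwise, training against sham and against usual treatment, so the three-arm figures overstate the problem. That is fair; the pairwise rows are the more relevant ones and they are lower. Usual treatment has no group training sessions, so equal clustering in all arms is the less favourable case.

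The remedy is not free. The mixed model is conservative, and at a very small ICC it can be further from 5% than the unadjusted test. This is a reason to prefer group means.

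A reader might infer that the error rate is in fact inflated by a known amount, or that the trial is underpowered by a known amount. The documents support neither. They give no ICC, and section 2.2 does not state the test or the correlation among measures behind 105, so the loss of power cannot be calculated. For the same reason one cannot say whether 150 is enough once clustering is allowed for.

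**Conclusion.** The point holds in conditional form and should be fixed. It is certain that session groups are nested in arms and that the plan does not account for them. The size of the harm is not known. Over ICCs of 0.02 to 0.10, which are assumptions, the true error of a nominal 5% test is 6.2-11.8% (three-arm) or about 6-10% (pairwise) with full groups. After 30% loss it is about 6-10% and 6-8% respectively. These figures assume a common ICC across arms and are lower if usual treatment has no clustering. The assurance about power after 30% loss holds only if there is no within-group correlation, because the increase from 105 to 150 leaves no margin beyond that loss.

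**What to change.** 1. In section 4, for the primary and secondary between-arm comparisons, account for the originally assigned session group nested in arm, even when a make-up session was attended elsewhere. Name one method in advance. Preferably compare group-mean change by arm, with up to 27 error df, or 18 for a pairwise contrast using only the two arms' groups, and fewer if a whole group is lost. The alternative is a mixed model with one common random session-group effect on change and small-sample df, which is valid but conservative.
2. In the cost-effectiveness bootstrap, resample whole session groups. Staff time is costed per session ("A professional with the category of Clinical Psychology for each session of cognitive training with 5 participants"), so costs as well as outcomes are shared within groups. State that 10 groups per arm make these intervals approximate.
3. In section 2.2, replace the assurance of power with a statement that power after 30% loss assumes no within-group correlation.

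The cost is SAP wording and one variable, the assigned session-group identifier. The documents do not say that it is recorded, so this should be confirmed. The statistical price is the widening shown above if the ICC is zero, fewer error df, and a less favourable power statement.
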